STATISTICAL ANALYSIS PLAN

Future Men's Boys Development Programme. A randomised controlled trial efficacy study

Cordis Bright

Principal investigators: [name], [name], [name], [name], [name]

Evaluation of Future Men's Boys

Development Programme

Statistical analysis plan

Evaluating institution: Cordis Bright **Principal investigator(s):** [name], [name], [name], [name], [name]

Project title	Future Men's Boys Development Programme. A randomised controlled trial efficacy study.		
Developer (Institution)	Future Men		
Evaluator (Institution)	Cordis Bright		
Principal investigator(s)	[name], [name], [name], [name], [name]		
SAP author(s)	[name], [name], [name]		
Trial design	Two-armed parallel randomised controlled trial with random allocation at the young person level		
Trial type	Efficacy study		
Evaluation setting	Six secondary schools in South London		
Target group	Boys aged 11 to 16 who are at risk of disengagement from school, exclusion or poor outcomes due to known adversity factors.		
Pupil age range and Key Stage	Aged 11 to 16, Key Stages 3 and 4.		
Number of participants	480 boys from six secondary schools		

Primary outcome and data source	School engagement, measured by the School Connectedness Questionnaire (Marsh and Randolph, 2020).		
	Relationships with peers, measured by the Strengths and Difficulties peer-relationship problems subscale (Goodman, 2005)		
	Emotional symptoms, based on the Strengths and Difficulties emotional symptoms subscale (Goodman, 2005)		
Secondary outcome and data source	Behavioural difficulties measured by the Strengths and Difficulties externalising behaviours score (Goodman, 2005)		
	Relationships with teachers, measured by the School Connectedness Teacher Bonding and Attachment subscale (Marsh and Randolph, 2020).		
	Relationship between project co-ordinator and young person, measured by the Social Support and Rejection Scale (Roffman et al., 2000).		

SAP version history

Version	Date	Changes made and reason for revision
1.1 [latest]	14 March 2025	Update made to the final sample size in Section 5 following completion of baseline data collection in February 2025.
1.0 [original]	July 2024	

2 Table of contents

1	SAP	SAP version history2			
2	2 Table of contents				
3	3 Introduction4				
4	Tria	al design	4		
	4.1	Overview	4		
	4.2	Research questions	7		
	4.3	Outcomes	7		
5	San	nple size calculations	8		
6	Ana	alysis	12		
	6.1	Overview	12		
	6.2	Primary outcome analysis	13		
	6.3	Secondary outcomes analysis	14		
	6.4	Subgroup analyses	16		
	6.5	Further analyses	17		
	6.6	Interim analyses and stopping rules	18		
	6.7	Longitudinal follow-up analyses	19		
	6.8	Imbalance at baseline	19		
	6.9	Missing data	20		
	6.10	Compliance	21		
	6.11	Intra-cluster correlations (ICCs)	22		
	6.12	Presentation of outcomes	22		
7	Ref	erences	23		

3 Introduction

This is the statistical analysis plan for an efficacy study, two-arm parallel randomised control trial (RCT) evaluation and implementation and process evaluation (IPE) of Future Men's Boys Development Programme (BDP). The BDP will be delivered across six schools in South London between September 2023 and July 2025 i.e. across two academic years. The efficacy study will run until March 2026.

The BDP is a targeted, manualised, social and emotional learning programme delivered across 12 one-to-one, 50 to 60-minute-long sessions. It aims to develop the social and emotional capacity and skills of boys in Years 7-11 who are at risk of exclusion and disengagement from schools, to improve school engagement and reduce the likelihood of exclusion.

The evaluation team are collecting a range of data throughout the trial. This includes:

- Self-reported outcomes measures, including the School Connectedness Questionnaire, the Strengths and Difficulties Questionnaire, and the Social Support and Rejection Scale.
- Demographic data provided by school partners, including age, sex, Free School Meal (FSM) eligibility, special educational needs and disabilities (SEND) data, English as an Additional Language (EAL) and care status.
- Activity and monitoring data collected by the Future Men delivery team.

This document sets out our planned analysis for each data type in more detail. The rest of this document is structured in the following way:

- Section 4: Trial design sets out the research questions, key outcomes and measures, and randomisation approach for the trial.
- Section 5: Sample size calculations presents the power calculations for the trial.
- Section 6: Analysis sets out the approach to analysis of primary outcomes, secondary outcomes, subgroup analysis, longitudinal analysis, further and interim analysis, missing data, compliance and outcomes presentation.

4 Trial design

4.1 Overview

The efficacy study is a two-arm, parallel randomised control trial (RCT). All young people who are referred into the project, who meet the eligibility criteria and who consent to be part of the evaluation will be allocated at random to a treatment or control group on a 1:1 basis.

Randomisation is conducted at the individual level, with stratification at the school level. Table 1 below presents an overview of the trial design.

Trial design, including number of arms		Two-arm parallel efficacy randomised controlled trial with random allocation at the young person level		
Unit of random	nisation	Individual young person		
Stratification variables		Secondary school		
Number of participants		480, i.e. 240 in the treatment group and 240 in the control group.		
	variable	School engagement		
Primary outcome	measure (instrument, scale, source)	School Connectedness Questionnaire (Marsh and Randolph, 2020).		
	variable(s)	Emotional symptoms; Relationships with peer Behaviour difficulties; Relationships with teacher Relationship between project co-ordinator an young person.		
Secondary outcome(s)		Relationships with peers, measured by the Strengths and Difficulties peer-relationship problems subscale (Goodman, 2005)		
		Emotional symptoms, measured by the Strengths and Difficulties emotional symptoms subscale (Goodman, 2005)		
		Behavioural difficulties, measured by the Strengths and Difficulties externalising behaviours score (Goodman, 2005)		

		Relationships with teachers, measured by the School Connectedness Teacher Bonding and Attachment subscale (Marsh and Randolph, 2020). Relationship between project co-ordinator and young person, measured by the Social Support and Rejection Scale (Roffman et al., 2000).		
Baseline for	variable	Self-report measure of school engagement		
primary outcome	measure (instrument, scale, source)	School Connectedness Questionnaire (Marsh and Randolph, 2020).		
	variable	Relationships with peers; Emotional symptoms; Behavioural difficulties; Relationships with teachers ¹ .		
	measure (instrument, scale, source)	Relationships with peers, measured by the Strengths and Difficulties peer-relationship problems subscale (Goodman, 2005)		
Baseline for secondary outcome		Emotional symptoms, based on the Strengths and Difficulties emotional symptoms subscale (Goodman, 2005)		
		Behavioural difficulties, measured by the Strengths and Difficulties externalising behaviours score (Goodman, 2005)		
		Relationships with teachers, measured by the School Connectedness Teacher Bonding and Attachment subscale (Marsh and Randolph, 2020).		

¹ Please note at baseline, we will not be using the Social Support and Rejection Scale as the young person will not have worked with the project co-ordinator prior to the BDP.

4.2 Research questions

The key research question of the efficacy study is:

'Does a targeted, social-emotional learning programme for boys at risk of disengagement and exclusion improve school engagement in comparison to business as usual?'

Additional research questions are:

- 1. **Delivery**: Can the BDP work under ideal circumstances?
- 2. **Impact**: a) What is the impact of the BDP? b) Do different sub-groups of young people have different outcomes, e.g. those from minoritized/marginalised groups?
- 3. **Unintended consequences**: Does the BDP have any unintentional consequences? If so, what are these? Do different groups of young people experience these differently?
- 4. **latrogenic effects**: Are there any serious negative effects attributed to the BDP on any outcomes?
- 5. Mechanisms: Which factors contribute most to the observed outcomes?

4.3 Outcomes

The primary outcome measure for the evaluation is school engagement measured by the School Connectedness Questionnaire (Marsh and Randolph, 2020). This measure was selected from the YEF outcomes framework in collaboration with YEF and Future Men colleagues.²

The secondary outcomes are that boys:

- Get along better with their peers, measured by the Strengths and Difficulties Questionnaire (SDQ) peer relationship problems sub-scale.
- Get along better with their teachers, measured by the SCQ teacher bonding and attachment subscale.
- Reduced behavioural difficulties, measured by the SDQ externalising behaviours score.

² For more information see: https://youthendowmentfund.org.uk/outcomes/.

- Reduction in emotional symptoms, measured by the SDQ emotional symptoms subscale.
- Have positive relationships with their project co-ordinator (control group) / significant adult (treatment group), measured by the Social Support and Rejection Scale total score.

Data for all measures is collected directly from boys by Future Men's research assistants and/or a project co-ordinator who is not delivering support using an online survey software. This is administered at baseline, 12 weeks and 24 weeks post-randomisation.

5 Sample size calculations

5.1 Overview

This section sets out:

- Power calculations for the whole cohort, which were conducted a priori as part of the initial trial design and co-design period.
- Power calculations for the subgroup of boys who are eligible for Free School Meals (FSM), which were conducted once randomisation had begun.
- An updated final sample size as of March 2025, following the completion of baseline data collection.

These calculations are summarised in Table 2 below and explained in more detail throughout this section.

Update: March 2025

Table 2 was updated in March 2025 following the completion of baseline data collection. It now sets out both the a priori power calculations completed as part of the trial design (protocol), and the final randomisation sample and MDES for the whole cohort and FSM subgroup following baseline data completion (randomisation). This shows that the trial has achieved its target baseline sample size. These calculations are explained in more detail in call out boxes in sections 5.2 and 5.3 below.

Table 2: Sample size calculations

		Protocol		Randomisation	
		Overall	FSM	Overall	FSM
Minimum Detectable Effect Size (MDES)		0.195	0.211	0.195	0.247
Pre-test/ post-test	level 1 (participant)	0.7	0.7	0.7	0.7
correlations	level 2 (cluster)	N/A	N/A	N/A	N/A
Alpha		0.05	0.05	0.05	0.05
Power		0.80	0.80	0.80	0.80
One-sided or two-sided?		Two-sided	Two-sided	Two-sided	Two-sided
	Intervention	211	180	212	132
Number of participants	Control	211	180	212	132
	Total	422	360	424	264

5.2 Whole cohort

We have determined the overall sample size for the trial a priori, in line with YEF guidance. These calculations suggest that a final sample size of 422 (211 per group) would ensure that the efficacy study is sufficiently powered to detect a statistically significant result if it exists (power = 0.80, two tailed, p < 0.05). Please note that our planned sample size for the trial is 480 boys, in line with Future Men's capacity to deliver the intervention. This provides buffer for attrition throughout the trial of 12% (58 boys). However, the final sample for the trial will not be finalised until randomisation is complete in April 2025. We will update Table 2 with

the final figures once they are known. Our approach to estimating the sample size for this efficacy study is conservative and has been influenced by the following:

- **YEF guidance.** YEF guidance suggests that efficacy study RCTs should have a Minimum Detectable Effect Size (MDES) of 0.20.
- Available data on the School Connectedness Questionnaire. The primary outcome measure for the study is school engagement, as measured by Marsh and Randolph's (2020) School Connectedness Questionnaire. In their validation study, Marsh and Randolph (2020) reported mean average scores, standard deviations and skew for each of the three SCQ sub-scales across two samples one for a sample of young people in general education, and one for a sample for young people experiencing emotional and behavioural disorders. Total scores and the associated standard deviation were not reported in Marsh and Randolph's (2020) paper, and data on pretest and post-test correlations has also not been published. As such, we have drawn from available data on similar measures (see below).
- Available data on similar measures. As described above, pre-test post-test correlations for the SCQ have not been published. Therefore, we draw from available data on the Student Engagement in Schools Questionnaire (Lam et al., 2014, p.38). For this scale, six month test-retest results were found to be 0.73 for the full-scale. In line with our conservative approach, we have therefore suggested a pre-test/post-test correlation of 0.7.

[figure not shown]
Table 2 at the start of this section presents power calculations which have been conducted in line with the above approach. These power calculations suggest that a sample size of 211 in each group (i.e. 422 in total) will be sufficiently powered to detect a statistically significant result if it exists (power = 0.80, two tailed, MDES = 0.195).³

[figure not shown]
Future Men's delivery capacity enables them to deliver the BDP intervention to a maximum of 240 boys over the duration of the study. With a control group allocated as close as is feasible to a one-to-one ratio, this means a total sample size of 480 boys is achievable under existing plans. Based on the power calculation above, this means even with attrition or non-completion of questionnaires for 38 boys (12%, which is slightly above YEF's desired target of no more than 10% attrition) the sample should be able to detect statistically significant differences if they exist.

³ These power calculations have been conducted using PowerUp. Available here: https://www.causalevaluation.org/power-analysis.html [Last accessed 17/06/2024].

Update: March 2025

Baseline data collection was completed in February 2025, with 483 baseline surveys collected (i.e, 3 more than our target of 480). Of these, 243 boys are in the BDP group, and 240 are in the signposting group, which is in line with our 1:1 allocation ratio target. The CONSORT diagram below presents this in more detail.

Maintaining the above assumptions of a 12% attrition rate, this suggests that the trial will have a final sample of 425 questionnaires at T2. Rounded down to 424 (i.e. 212 in each group), power calculations suggest that this will result in a final MDES of 0.195.

5.3 Free School Meals subgroup

In line with EEF/YEF requirements, we have also conducted power calculations relating to the subgroup of boys who are eligible for Free School Meals (FSM). These calculations were conducted as part of the finalisation of this statistical analysis plan, i.e. once the trial had begun.

We have estimated that 75% of the overall cohort will be eligible for Free School Meals. This is based on the available demographic data for the boys who have been onboarded to the trial as of 4th January 2024. This shows that 75% (87 boys, n=116) are in receipt of FSM. Assuming that this trend continues, we estimate that 360 boys (i.e., 75% of the overall sample

of 480) will be eligible for FSM. This translates to 180 boys in the treatment group, and 180 boys in the control group. However, we will revisit this once baseline data collection is complete and the characteristics of the entire cohort are known.

Maintaining the assumptions outlined above (power = 0.80, two tailed, p < 0.05), a sample size of 360 will be powered to detect an MDES of 0.211 for this subgroup if it exists. Section 6.4 provides more information on our approach to subgroup analyses for the FSM cohort.⁴

Update: March 2025

Of the 483 boys with a baseline survey, 301 boys (62%) were reported to be eligible for free school meals by school partners. Of these, 145 boys (48%) are in the BDP group, and 156 boys (52%) are in the signposting group.

Maintaining the above assumptions of 12% attrition rate, this suggests that the trial will have a final sample of 264 questionnaires at T2 for boys who are eligible for Free School Meals. Power calculations suggest that this will result in a final MDES of 0.247 for this subgroup.

6 Analysis

6.1 Overview

This section presents a draft analytical approach for the efficacy study. This is because randomisation is still being undertaken and baseline data is not complete. As such, we currently do not know the structure of the baseline data, and this should be considered when interpreting the following analysis plan. Once all baseline data has been collected, we will revisit and finalise the analysis plan. This will be specified and documented before follow-up outcomes data has been collected, and will also include a baseline CONSORT diagram.

All analysis will be conducted on an intent-to-treat basis in line with YEF and EEF guidance. This means that participants will be analysed according to their allocation, regardless of whether they received the BDP or not. This provides the most conservative estimate of impact, as it captures the impact of offering the intervention for those who do and do not comply, and helps to fully preserve the benefits of randomisation (Torgerson and Torgerson, 2008). This approach is particularly relevant for policymakers and commissioners, i.e. those who may roll out an intervention but do not have control over take-up across the system.

⁴ These power calculations have been conducted using PowerUp. Available here: https://www.causalevaluation.org/power-analysis.html [Last accessed 17/06/2024].

The analytical approach has been developed a priori and will be conducted in SPSS. The syntax for all analysis will be provided once it has been developed after all data has been collected.

6.2 Primary outcome analysis

The primary outcome is an improvement in school engagement at the individual level, as measured by the School Connectedness Questionnaire (SCQ). All young people will have completed the SCQ before randomisation, and at around 12 weeks and 24 weeks post randomisation. The primary outcome time point is 12 weeks post-randomisation.

About the School Connectedness Questionnaire (Marsh and Randolph, 2020)

The SCQ contains 10 items. Each item is marked either Not True, Somewhat True, or True, which are assigned a score of 1 to 3 respectively. It consists of three subscales:

- 1. Teacher bonding and attachment (3 items);
- 2. Peer bonding and attachment (4 items); and
- 3. School engagement (3 items).

The score for each subscale is the sum of its items. The primary outcome measure for this trial is the sum of the three subscale scores, and analysis of each subscale score will also be presented separately.

There is considerable debate about best practice when it comes to the analysis of data from RCTs. For example, Twisk et al. (2018) advocate for utilising longitudinal analysis of covariance or a repeated measures analysis without the treatment variable, but with the interaction between treatment and time in the model controlled for. They argue that failure to control for baseline differences in outcomes between the groups can lead to biased treatment estimates. Alternatively, others have cautioned against this approach (Sen, 2013).

Based on our understanding of the literature, our analysis of impact on the primary outcome will be conducted using a fixed effects analysis of co-variance (ANCOVA) model, which accounts for the stratification factor used in randomisation.

We will use the following model:

$$Y_i = \beta_0 + \beta_1 Baseline_i + \beta_2 Group_i + \delta School_k + \varepsilon_i \in N(0, \sigma^2)$$

For i = 1, ..., n pupils per school, and k = 1, ..., K schools.

Where:

• Y_i is the school engagement subscale score as measured by the SCQ.

- *Baseline_i* is the baseline outcome measure of the school engagement subscale for pupil *i*.
- *Group*_i is a dummy variable for allocation group, i.e. 1 for the treatment group and 0 for the control group.
- β_2 is the average treatment effect, i.e. the primary parameter of interest for the trial.
- School_k is a vector of K 1 binary school dummy variables.
- ε_i is the error/residual.
- σ^2 is the variance.

This analysis is designed to evaluate the differences in school engagement between boys in the BDP group, and boys in the business-as-usual group. Specifying the model upfront will ensure analysis avoids the "fishing problem" and the "curse of dimensionality" (Humphreys et al 2013; Hayes 2011).

We will run robustness checks to assess the underlying assumptions for ANCOVA. This will include assessing normality of the data using histograms and K-S tests. If the data does not meet these assumptions, we will run a non-parametric ANCOVA analysis. This will be determined once all data has been collected.

In line with the findings from Marsh and Randolph's (2020) original validation paper for the SCQ, it is possible that the baseline and outcome variables may be positively skewed. Skew will be assessed using the traditional criteria based on their distribution (i.e., skews of greater or equal to 1.0 or less than or equal to -1.0). Arguably, it is more desirable to use the appropriate modelling of non-normally distributed variables (e.g., Akram et al., 2023), than it is to transform the data.

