6.8 Imbalance at baseline

If randomisation has been successful, both treatment and business-as-usual groups should be equivalent at baseline. As such, any imbalance will have occurred by chance. To check for and monitor imbalance at baseline, we will produce a table of descriptive characteristics for all young people at baseline. We will also produce an equivalent table for those included in the final analysis sample, to check whether any attrition experienced throughout the trial may have introduced an imbalance. These descriptive characteristics will include:

- Age.
- Sex.
- Ethnicity.
- Free school meal eligibility.
- English as an additional language.
- SEND status.
- Baseline SCQ scores.

Baseline SDQ scores.

Data on pupil characteristics is provided by school partners through the initial referral form. We will present a cross-tabulation of counts and percentages for each category above against allocation group. For continuous variables, we will present the means and standard deviation. This analysis will be used to inform our understanding of the extent to which our initial sample was balanced across the two groups, and whether any attrition experienced throughout the trial has introduced an imbalance. We will discuss any differences and their implications in the final report.

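### Optional precision gain: age and baseline SDQ are already collected but are not in the default primary ANCOVA

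*SAP*

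**What the plan says.** SAP section 6.2 sets the primary analysis as a "fixed effects analysis of co-variance (ANCOVA) model, which accounts for the stratification factor used in randomisation". Its terms are one baseline score, allocation group and a set of school dummies. Section 6.3 carries the same model to each secondary outcome, with that outcome's own baseline.

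Other baseline information is available:

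- Section 3 lists "Demographic data provided by school partners, including age, sex, Free School Meal (FSM) eligibility" among the data collected. Section 6.8 adds: "Data on pupil characteristics is provided by school partners through the initial referral form". Under section 4.1, referral comes before allocation.
- Table 1 in section 4.1 lists the baseline measures for the secondary outcomes as "Relationships with peers; Emotional symptoms; Behavioural difficulties; Relationships with teachers". Three of these are SDQ scores: peer problems, emotional symptoms and externalising. By the scoring in section 6.3, externalising is conduct plus hyperactivity, so the three together give the SDQ total difficulties score.

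Section 6.8 puts age and baseline SDQ in the balance table. Section 6.9 provides one route into the primary model: covariates on which missing outcome data are found to depend.

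On power, section 5.2 gives "power = 0.80, two tailed, MDES = 0.195" for 422 boys. After baseline collection it states: "Rounded down to 424 (i.e. 212 in each group), power calculations suggest that this will result in a final MDES of 0.195". The baseline correlation is an assumption: "we have therefore suggested a pre-test/post-test correlation of 0.7". It is borrowed from another engagement scale, because no such figure has been published for the SCQ.

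**The concern.** The boys are aged 11 to 16 and were referred because of risk of disengagement, exclusion or poor outcomes. Age and baseline emotional and behavioural scores may well predict later school connectedness beyond what the baseline connectedness score captures. If they do, leaving them out of the default model gives a wider interval for the treatment effect than the data allow, and leaves chance imbalance on them uncorrected.

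The projected MDES of 0.195 is close to the guidance figure of 0.20 in section 5.2, and it rests on a borrowed correlation. A gain that needs no further recruitment is therefore worth considering.

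The Social Support and Rejection Scale is a special case. The footnote to Table 1 says it is not measured at baseline, so the section 6.3 model has no baseline term to use. As written, that outcome has no participant-level adjustment at all.

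**Working it through.** **Inputs from the SAP** (section 5.2 and Table 2): two-sided alpha 0.05; power 0.80; pre/post correlation 0.7; 1:1 allocation; 422 boys at the protocol stage and 424 at the randomisation stage. 
**Input not in the SAP:** the share *p* of residual variance explained by age and baseline SDQ, given the baseline score. This is an assumption, varied from 0% to 10%.

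**Step 1. Reproduce the plan's figure.** With r = 0.7, the residual variance is 1 − 0.49 = 0.51 of the outcome variance.

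MDES = (t₀.₉₇₅ + t₀.₈₀) × √[0.51 / (0.25 N)], where the two t quantiles sum to about 2.808.

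- N = 422: 2.808 × √(0.51/105.5) = 0.1952
- N = 424: 2.808 × √(0.51/106) = 2.808 × 0.06936 = 0.1948

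Both round to the stated 0.195. The normal-approximation sample size for 0.195 is 211 per group, also as stated.

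**Step 2. Add the covariates.** The residual variance becomes 0.51 × (1 − p). The model now has 8 parameters (intercept, baseline, group and five school dummies) and would have 10, so the residual degrees of freedom go from 416 to 414. The sum of the t quantiles stays at 2.808. Power is from the noncentral t distribution with 212 per group. The equivalent sample size is 424/(1 − p).

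| Assumed p | Residual variance | MDES | Power at 0.195 | Equivalent N |
|---|---|---|---|---|
| 0% | 0.510 | 0.195 | 80.1% | 424 |
| 2% | 0.500 | 0.193 | 80.9% | 433 |
| 5% | 0.485 | 0.190 | 82.1% | 446 |
| 10% | 0.459 | 0.185 | 84.1% | 471 |

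If the covariates explain nothing, the loss of two degrees of freedom does not change any figure to the precision shown.

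**Step 3. How much margin is there already?** At an effect of 0.20 the current model has about 82% power with 424 boys. With all 483 boys followed up, power at 0.195 would be 85.1%.

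**Step 4. Does the change protect against a wrong correlation?** Only slightly. With 424 boys the MDES exceeds 0.20 once r falls below about 0.68. If p is 5% the threshold is about 0.66, and if p is 10% about 0.63. At r = 0.6, power at 0.195 is 70.9% (normal approximation), and covariates with p = 5% raise it only to 73.1%.

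**The case against.** The strongest reply is that nothing here is wrong. A pre-specified ANCOVA on the baseline outcome and the stratification factor is unbiased under randomisation and matches the power calculation. Section 6.2 also gives a reason for fixing a single model in advance. All of that stands, and a reader who inferred that the primary model is faulty or biased would go further than the SAP supports.

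The benefit is also assumed. No section gives a correlation of age or SDQ with follow-up SCQ, and the baseline score is already taken to explain 49% of the variance. The 10% end of the range needs a multiple partial correlation of about 0.32 (√0.10) beyond that. This stands too, and is why the result is a range that starts at zero.

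Three other inferences are tempting but unsupported:

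- *That the trial has no power margin.* An MDES is defined at the chosen power, so 80% at 0.195 is true by construction. Power at 0.20 is about 82%, and 424 is already net of 12% attrition.
- *That age and SDQ serve only the balance table.* SDQ baselines enter the SDQ outcome models under section 6.3, and section 6.9 can bring covariates into the primary model.
- *That the covariates would make up for a low SCQ correlation.* Step 4 shows that they would not.

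Timing is a fair objection. Section 5.3 reports 116 boys onboarded by 4 January 2024, and the primary time point is 12 weeks. By version 1.1 of March 2025, much of the follow-up was therefore due. A change to the primary model is defensible only if outcomes have not been seen by arm. This limits how the change is made; it does not remove the case for it.

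**Conclusion.** The point holds as an optional improvement, not as an error. The default primary model is valid but leaves out two baseline variables already collected. Pre-specifying them would bring the MDES at 424 boys from 0.195 to between 0.195 and 0.185, and power at 0.195 from 80% to between 80% and 84%. These figures rest on the plan's r = 0.7 and 12% attrition, and on an assumed 0% to 10% of residual variance explained. The SAP supports no single value in that range.

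The secondary benefit is a rule for the Social Support and Rejection Scale, which has no baseline. Fixing the covariates in advance also makes part of the section 6.9 adjustment independent of the missingness results.

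Two neighbouring matters limit what the change can achieve:

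- Section 6.2 names the sum of three subscales as the primary outcome but defines the model's outcome and baseline as the school engagement subscale. That conflict is more serious and should be settled first.
- The standard error for the effect size in section 6.12 has no residual-variance term, so covariate adjustment would narrow the interval for the model coefficient but not the interval for g as defined there.

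**What to change.** In section 6.2, add age (or school year) and baseline SDQ total difficulties as fixed covariates in the primary model. In section 6.3:

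- for SDQ outcomes, use the outcome's own baseline plus age and baseline SCQ;
- for the SCQ teacher subscale, follow the primary model;
- for the Social Support and Rejection Scale, use age plus baseline SCQ and baseline SDQ.

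Keep the current model as a stated sensitivity analysis.

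Conditions on the change:

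1. Lock and date it before any outcome data are seen by arm, and say so in the version history.
2. Confirm that the SDQ was completed before randomisation. Section 6.2 states this for the SCQ; for the other measures section 4.3 says only that they are given at baseline.
3. State how missing values of the added covariates are handled, consistently with the multiple-imputation rule in section 6.9, so that no boy is dropped because of them.

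Cost: SAP wording, two terms in syntax that section 6.1 says is still to be written, and two degrees of freedom out of more than 400. No new data are needed. The downside is a slightly longer model and one more missing-data rule.

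### Section 6.2 declares the SCQ total score as the primary outcome, but the primary ANCOVA is written for the 3-item school engagement subscale

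*SAP*

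**What the plan says.** The SCQ box in Section 6.2 describes the instrument: "The SCQ contains 10 items", marked in three categories "which are assigned a score of 1 to 3 respectively". The items form three subscales: teacher bonding (3 items), peer bonding (4 items) and "School engagement (3 items"). On the primary outcome the box is explicit: "The primary outcome measure for this trial is the sum of the three subscale scores". It adds that each subscale will also be reported separately.

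The model follows in the same section. Its dependent variable "is the school engagement subscale score as measured by the SCQ". Its covariate "is the baseline outcome measure of the school engagement subscale for pupil" i. The coefficient of allocation, beta_2, "is the average treatment effect, i.e. the primary parameter of interest for the trial".

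Section 5.2 supports the pre/post correlation of 0.7 with one figure, from a different engagement questionnaire: "six month test-retest results were found to be 0.73 for the full-scale".

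**The concern.** Two sentences in one section name two different primary variables. The equation is what an analyst will code. Section 6.1 says the SPSS syntax will be written only after all data are in, so no existing code settles which variable is meant.

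If the equation is followed literally, the trial's headline estimate is for a 3-item score that the box treats as supplementary, and no model equation in Section 6 names the declared primary outcome as its dependent variable. The ambiguity also spreads. Section 6.4 reuses the variables of the 6.2 model, 6.7 speaks only of school engagement, and the second stage in 6.10 is the 6.2 model with predicted compliance substituted for allocation.

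The likely cause is the name: school engagement is both the primary construct and the title of one SCQ subscale. The slip is in both model terms, so it is not one stray word. The version history for 1.1 records only the sample-size update in Section 5.

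**Working it through.** **The two variables (Section 6.2).** Items: 3 + 4 + 3 = 10, each scored 1 to 3.

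| | Declared primary outcome | Y and Baseline in the model |
|---|---|---|
| Score | Sum of three subscales | School engagement subscale |
| Items | 10 | 3 |
| Range | 10×1 to 10×3 = 10 to 30 | 3×1 to 3×3 = 3 to 9 |

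**Which one the SAP intends.** Section 6.3 runs the model on the three individual subscales in addition to the main analyses. That makes sense only if the primary analysis is not already one of them. The summary table, Table 1 and Section 4.3 give the primary measure as the SCQ with no subscale, yet name the teacher bonding subscale where a subscale is meant. All of this favours the total.

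**The plan's own power figure.** Inputs from Table 2: two-sided alpha 0.05, power 0.80, r = 0.7, 1:1 allocation.

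MDES = (t.975 + t.80) × sqrt[(1 − r²) / (0.25 N)], df = N − 3, multiplier 2.808.

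- N = 422: 2.808 × sqrt(0.51 / 105.5) = 2.808 × 0.0695 = 0.1952
- N = 424: 2.808 × sqrt(0.51 / 106) = 2.808 × 0.0694 = 0.1948

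Both round to the stated 0.195. The reverse calculation, 2 × 0.51 × (1.960 + 0.842)² / 0.195² = 210.5, gives 211 per arm. The plan's figures reproduce. They are in SD units and depend on the outcome only through r.

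**If the subscale were meant.** The SAP gives no correlation for it, so r must be assumed. Power at 0.195 is Φ(0.195/se − 1.96), with se = sqrt[(1 − r²)/106] at N = 424.

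| Assumed r | MDES | Power at 0.195 |
|---|---|---|
| 0.70 (the plan's value) | 0.195 | 80% |
| 0.66 | 0.205 | 76% |
| 0.60 | 0.218 | 71% |
| 0.50 | 0.236 | 64% |
| 0.44 | 0.245 | 61% |

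The ends of the range come from scaling r = 0.7 by the ratio of subscale to total reliability, assuming equal true-score stability for both scores.

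- Low end: total reliability 0.75 and all 10 items interchangeable. Spearman-Brown with k = 0.3 gives 0.3 × 0.75 / (1 − 0.7 × 0.75) = 0.474, and r = 0.7 × 0.474 / 0.75 = 0.44.
- High end: inter-item correlation 0.5 within and 0.2 between subscales. There are 12 within-subscale and 33 between-subscale pairs, so the mean is (12 × 0.5 + 33 × 0.2) / 45 = 0.28. Alpha for 10 items is 2.8 / 3.52 = 0.795, and for 3 items 1.5 / 2 = 0.75. Then r = 0.7 × 0.75 / 0.795 = 0.66.

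**The case against.** The fair reply is that this is a wording slip that a careful analyst would resolve correctly. The box is explicit, Section 6.3 agrees with it, and Section 6.1 calls the analytical approach a draft to be finalised before follow-up. The point about intent stands and is adopted here. It does not remove the need for a correction: the contradiction is in the operative definition of the primary model, and version 1.1 reports no change outside Section 5.

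A reader might infer that the trial is underpowered, or that 0.195 is wrong. The documents do not support that. The calculation is a standardised one and is arithmetically sound. Its r = 0.7 is borrowed from another questionnaire, so it is an assumption for the SCQ total as well. No subscale correlation is given, so a loss of power is not demonstrated. Treating all 10 items as interchangeable also probably exaggerates the loss, because items within a subscale usually correlate more strongly than items across subscales.

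A reader might also infer that either score could equally be reported as primary once results are known. That goes too far, since the balance of the text favours the total. What remains is that a literal reading of the equation gives the other score.

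**Conclusion.** The contradiction is certain and rests on no assumption: the declared primary outcome and the modelled outcome in Section 6.2 are different variables, and the error is in both the dependent variable and the baseline covariate. It must be corrected because it decides what the confirmatory test is.

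The consequence for power is conditional. With the total score as outcome, there is none. With the subscale as outcome, r = 0.7 has no stated support, and the range of 61% to 76% power is an illustration under the reliability assumptions shown above. It is not an estimate for this trial.

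**What to change.** In Section 6.2, define Y_i as the SCQ total score (sum of the three subscale scores) at 12 weeks and Baseline_i as the SCQ total score at baseline. Carry the same definition into 6.4, 6.7 (with the total at 12 and 24 weeks as outcome) and 6.10. Keep the three subscales, including school engagement, as additional analyses under 6.3. Record the change in the version history before any outcome is compared by arm.

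The cost is a few words. Table 2 needs no change on this account.

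If the subscale is what the evaluators intend, the outcome definition in the box must change instead, and Section 5.2 must justify a pre/post correlation and a detectable effect for a 3-item score.
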